6.14.7. Histopathology

Biopsies will be collected during endoscopy procedures at Screening, Week 12, and Week 52. The Central Readers will review the images in a blinded fashion and determine the following scores:

- Global Histologic Disease Activity Score (GHAS; D’Haens et al. 1998): assesses the extent and severity of histologic inflammation in colonic or ileal biopsy samples in CD. Factors include epithelial and architecture changes, inflammatory cell infiltrates, erosions or ulcers, granulomas, and an adjustment for the number of biopsy samples affected.
- Robarts Histopathology Index (RHI; Mosli et al. 2017): a new evaluative index that is designed to be reproducible and responsive to clinically meaningful change in disease activity over time. The total RHI score ranges from 0 (no disease activity) to 33 (severe disease activity).

Descriptive statistics will be presented for the changes from baseline in GHAS and RHI for Safety Population Periods 1 and 2. The definition for histological mucosal healing based on GHAS and RHI (that is, the cut-off for CD) has not been determined; details of the analyses will be documented when specified by Robarts Clinical Trials (ROBARTS).

6.14.8. Special Safety Topics

6.14.8.1. Abnormal Hepatic Tests

Analyses for laboratory analyte measurements are described in Section 6.14.3. This section describes additional analyses for the topic.

The percentages of subjects with the following elevations in hepatic laboratory tests at any time will be summarized between treatment groups:

- The percentages of subjects with a alanine aminotransferase (ALT) measurement greater than or equal to 3 times (3X), 5 times (5X), and 10 times (10X) the performing lab ULN during the treatment period will be summarized for all subjects with a postbaseline value and for subsets based on various levels of baseline value.
 - The analysis of 3X ULN will contain 4 subsets:
 - subjects whose non-missing maximum baseline value is less than or equal to 1X ULN
 - subjects whose maximum baseline is greater than 1X ULN but less than 3X ULN
 - subjects whose maximum baseline value is greater than or equal 3X ULN
 - subjects whose baseline values are missing
 - The analysis of 5X ULN will contain 5 subsets:
 - subjects whose non-missing maximum baseline value is less than or equal to 1X ULN
 - subjects whose maximum baseline is greater than 1X ULN but less than 3X ULN
 - subjects whose maximum baseline is greater than or equal to 3X ULN but less than 5X ULN
 - subjects whose maximum baseline value is greater than or equal to 5X ULN
 - subjects whose baseline values are missing
 - The analysis of 10X ULN will contain 6 subsets:
 - subjects whose non-missing maximum baseline value is less than or equal to 1X ULN
 - subjects whose maximum baseline is greater than 1X ULN but less than 3X ULN
 - subjects whose maximum baseline is greater than or equal to 3X ULN but less than 5X ULN
 - subjects whose maximum baseline is greater than or equal to 5X ULN but less than 10X ULN

- subjects whose maximum baseline value is greater than or equal to 10X ULN
- subjects whose baseline values are missing
- The percentages of subjects with an aspartate transaminase (AST) measurement greater than or equal to 3X, 5X, and 10X the performing lab ULN during the treatment period will be summarized for all subjects with a postbaseline value and for subsets based on various levels of baseline, as described above for ALT.
- The percentages of subjects with a total bilirubin measurement greater than or equal to 2 times (2X) the performing lab ULN during the treatment period will be summarized for all subjects with a postbaseline value, and subset into 4 subsets:
 - subjects whose non-missing maximum baseline value is less than or equal to 1X ULN
 - subjects whose maximum baseline is greater than 1X ULN but less than 2X ULN
 - subjects whose maximum baseline value is greater than or equal to 2X ULN
 - subjects whose baseline values are missing

Maximum baseline will be the maximum non-missing observation in the baseline period. The maximum value will be the maximum non-missing value from the treatment period. Planned and unplanned measurements will be included.

These analyses will be conducted for Safety Population Period 1, Safety Population Period 2, Safety Population All SC LY, and Safety Population All LY.

Individual graphical subject profiles will be prepared for subjects with an ALT or AST measurement greater than or equal to 5X ULN or with an alkaline phosphatase (ALP) measurement greater than or equal to 2X ULN. A graphical subject profile will be created for any subject meeting the criteria from the Safety Population (any phase, any medication). The graphical subject profile will include demographics, disposition, and a display of study drug exposure, AEs, medications, and liver-related measurements over time. The review for these subjects includes an assessment of the proximity of any ALT or AST elevation to any total bilirubin elevation, ALP levels, gamma-glutamyl transpeptidase (GGT) levels, other potential causes, and the temporal association with events such as nausea, vomiting, anorexia, abdominal pain, or fatigue.

A plot of maximum postbaseline ALT versus maximum postbaseline total bilirubin will be created that includes all subjects from the Safety Population (any phase, any medication). Each subject with at least 1 postbaseline ALT and total bilirubin contributes 1 point to the plot. The maximum ALT measurement divided by ULN and the maximum total bilirubin measurement divided by ULN during the treatment period are used. The measurements do not need to be taken at the same blood draw. Symbols will be used to indicate treatments (concentrated when multiple treatments are taken).

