8.1. Discontinuation from Study Treatment

8.1.1. *Permanent Discontinuation from Study Treatment*

Discontinuation of the investigational product for abnormal liver tests should be considered by the investigator when a subject meets one of the following conditions after consultation with the Lilly designated medical monitor:

- ALT or AST >8xULN
- ALT or AST >5xULN for more than 2 weeks
- ALT or AST >3xULN and TBL >2xULN or prothrombin time >1.5xULN
- ALT or AST >3xULN with the appearance of fatigue, nausea, vomiting, right upper-quadrant pain or tenderness, fever, rash, and/or eosinophilia (>5%)
- ALP >3xULN
- ALP >2.5xULN and TBL >2xULN
- ALP >2.5xULN with the appearance of fatigue, nausea, vomiting, right quadrant pain or tenderness, fever, rash, and/or eosinophilia (>5%).

Subjects may discontinue treatment for any of the reasons noted above, or for other reasons such as the development of a serious adverse event. To better communicate patient flow throughout the study, different study period situations are provided below:

- Subjects who discontinue the investigational product in Period 1 or Period 2 may continue in the study according to the visit schedule (Section 2).
- At Week 52/Visit 18, subjects who have previously discontinued the investigational product will continue to Visit 801 of the Follow-up Period.
- Subjects who discontinue the investigational product in Period 3 may continue in Period 3 and then proceed to Week 104/Visit 801 of the Follow-up Period.

Investigational product is to be discontinued for patients who experience clinically significant systemic hypersensitivity events (such as anaphylaxis) following administration of investigational product.

8.1.2. *Discontinuation of Inadvertently Enrolled Subjects*

If the sponsor or investigator identify a subject who did not meet enrollment criteria and was inadvertently enrolled, a discussion must occur between the sponsor CRP and the investigator to determine if the subject may continue in the study. If both agree it is medically appropriate to continue, the investigator must obtain documented approval from the sponsor CRP to allow the inadvertently enrolled subject to continue in the study with or without treatment with investigational product.

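### The SAP's hepatic profile trigger has no bilirubin limb, so some subjects meeting the protocol's combined ALT/AST and bilirubin condition are neither reviewed for timing nor counted by arm

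*SAP*

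**What the plan says.** Protocol 8.1.1 gives conditions under which the investigator should consider discontinuing study drug after consulting the medical monitor. One is "ALT or AST >3xULN and TBL >2xULN or prothrombin time >1.5xULN". ALT and AST count equally in it.

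SAP 6.14.8.1 plans three kinds of hepatic display:

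- **Tables.** ALT and AST at ≥3×, ≥5× and ≥10×ULN, and total bilirubin at ≥2×ULN, each analyte on its own, for all four safety populations. The tables are split by baseline level; the bilirubin table has a stratum for "subjects whose maximum baseline value is greater than or equal to 2X ULN".
- **Profiles.** The transaminase limb of the trigger is: "Individual graphical subject profiles will be prepared for subjects with an ALT or AST measurement greater than or equal to 5X ULN". The only other limb is ALP ≥2×ULN. The review is then described: "The review for these subjects includes an assessment of the proximity of any ALT or AST elevation to any total bilirubin elevation".
- **Plot.** "A plot of maximum postbaseline ALT versus maximum postbaseline total bilirubin will be created", with one point per subject. On treatment: "Symbols will be used to indicate treatments". On timing: "The measurements do not need to be taken at the same blood draw". AST is not plotted.

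SAP 6.14.3 adds single-analyte shift displays, spaghetti plots and a listing of abnormal laboratory findings by subject, treatment, date and analyte.

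**The concern.** The review is meant to judge whether a transaminase rise and a bilirubin rise in the same subject came close together. Whether a subject enters it depends on the size of the ALT, AST or ALP value alone. A subject with isolated ALP of 2×ULN and normal bilirubin is profiled. A subject with AST 4×ULN and bilirubin 3×ULN may not be, although that subject has the pairing the review assesses and meets a condition the protocol treats as grounds for considering withdrawal of drug.

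At stake is how completely the safety evaluation, a secondary objective, reports this pattern. Single-analyte percentages cannot show whether the same subject had both rises. For AST-driven cases, no display in the section shows the pair at all.

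**Working it through.** The plan states no figure on this point, so the check applies its rules to cases. All values are multiples of ULN.

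**Rules**

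- Protocol condition (8.1.1, bilirubin limb): (ALT > 3 or AST > 3) and TBL > 2.
- SAP profile trigger (6.14.8.1): ALT ≥ 5 or AST ≥ 5 or ALP ≥ 2.
- Recognisable as a pair on the plot: ALT ≥ 3 and TBL > 2. These reference lines are an assumption; the SAP gives none.

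**The gap.** Meeting the first rule and failing the second means ALT or AST > 3, both < 5, ALP < 2 and TBL > 2.

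**Four illustrative cases**

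| Case | ALT | AST | ALP | TBL | Meets 8.1.1 | Profiled | Pair visible on plot |
|---|---|---|---|---|---|---|---|
| A | 4 | 2 | 1.2 | 3 | yes | no | yes, at (4, 3) |
| B | 2 | 4 | 1.2 | 3 | yes | no | no, at (2, 3) |
| C | 2 | 4 | 2.2 | 3 | yes | yes (ALP) | no |
| D | 2 | 6 | 1.2 | 3 | yes | yes (AST) | no |

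Case B plots like an isolated bilirubin rise. It is not profiled, and it is counted once in the AST table and once in the bilirubin table with nothing to link the two.

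**Grid check.** Take ALT and AST each in {1, 2, 3.5, 4.5, 5, 8}, TBL in {1, 1.5, 2.1, 3} and ALP in {1, 1.5, 2, 3}.

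- Meeting 8.1.1: of 6 × 6 = 36 ALT/AST pairs, 2 × 2 = 4 have both ≤ 3, leaving 32. With 2 TBL values above 2 and 4 ALP values, 32 × 2 × 4 = 256.
- Not profiled: of 4 × 4 = 16 pairs with both < 5, the same 4 drop out, leaving 12. With 2 TBL values and 2 ALP values below 2, 12 × 2 × 2 = 48.
- Of these 48, visible on the plot (ALT 3.5 or 4.5): 2 × 4 × 2 × 2 = 32.
- Not recognisable on the plot (ALT 1 or 2, AST 3.5 or 4.5): 2 × 2 × 2 × 2 = 16.

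So 256 − 48 = 208 of 256 combinations are reviewed under the current trigger. Adding (ALT or AST ≥ 3 and TBL ≥ 2) captures all 256, because > 3 with > 2 implies ≥ 3 with ≥ 2. The grid shows which combinations the rules miss. It says nothing about how often they occur.

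**What the single-analyte tables can tell.** In any arm, the number with both AST ≥ 3 and TBL ≥ 2 is at most the smaller of the two separate counts. If either is zero, the joint count is zero. If each were 2, the joint count could be 0, 1 or 2, and the tables would not say which.

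**The case against.** The strongest reply is that no rule is broken. Protocol 8.1.1 governs treatment and SAP 6.14.8.1 governs displays; nothing requires one to mirror the other. The SAP trigger also passes over the protocol's condition of ALT or AST >3×ULN with symptoms, so it was probably not built to follow 8.1.1. SAP 6.1 leaves room for additional exploratory analyses. That is all correct, and the two documents do not conflict. But the proximity of the two rises is the SAP's own review question, and leave to do more is not a plan to select these subjects.

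Several mitigations also stand in part:

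- ALT-driven cases can be read off the plot with a treatment symbol. The plot pools all phases and treatments, however, and merges symbols when a subject took more than one. Placebo subjects who continue treatment move to 1000 mg IV in Period 2, so a merged symbol does not show which treatment the rise occurred on.
- The separate counts bound the joint count, and settle it when either is zero.
- The dated listing allows AST and bilirubin to be paired by hand. Spaghetti plots and visualization tools may help, but the SAP does not say that they select or pair these analytes.
- Every subject in the gap has bilirubin above 2×ULN, which alone triggers monitoring and sponsor consultation under Protocol 9.5.5. That is patient care, not a planned analysis.
- Protocol 10.3.7 refers to a separate trial-level safety review plan, which is not available here and may cover the combination.

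Finally, about 180 subjects enter under a general limit of 2×ULN for ALT, AST and bilirubin, and nothing in the documents says that even one such case should be expected. This limits the weight of the point but does not close the gap.

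**Conclusion.** The concern holds, as a minor one. The planned proximity review leaves out subjects with ALT or AST above 3×ULN but both below 5×ULN, ALP below 2×ULN and bilirubin above 2×ULN, and no table in SAP 6.14.8.1 counts the combination by arm. Within that region, cases with ALT ≥3×ULN show as a pair on the plot without timing. Cases with ALT below 3×ULN do not, and would have to be assembled from the listing.

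How many subjects this affects is unknown. No data are lost, patient monitoring is unaffected, and no efficacy result or error rate depends on it. The conclusion rests on the stated rules of SAP 6.14.8.1 and 6.14.3 and, for the plot, on reference lines at 3× for ALT and 2× for bilirubin.

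**What to change.** In SAP 6.14.8.1:

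1. Extend the profile trigger to: ALT or AST ≥5×ULN, or ALP ≥2×ULN, or ALT or AST ≥3×ULN with total bilirubin ≥2×ULN. These cuts match the SAP's own tables and cover the protocol's limits.
2. Add one row by treatment group, for the same four safety populations, counting subjects whose maximum ALT or AST is ≥3×ULN and whose maximum total bilirubin is ≥2×ULN in the treatment period. Show separately those whose maximum baseline bilirubin was already ≥2×ULN, as the bilirubin table does; inclusion criterion 11 makes separate provision for Gilbert's syndrome. Footnote that the row uses maxima and does not show that the rises coincided; timing is judged from the profiles.

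The prothrombin-time alternative in 8.1.1 can be left out, because prothrombin time is not among the scheduled tests in Protocol Appendix 2.

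With these changes, cases A to D are all profiled and counted. The cost is one clause, one table row and possibly a few more profiles, all from data already collected.

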6.14.8.2. Infections

Infections will be defined using the PTs from the MedDRA Infections and Infestations SOC.

Treatment-emergent infections will be analyzed according to various groups of infectious events including:

- all infections
 - all PTs in the Infections and Infestations SOC by maximum severity,
- serious infections
 - all PTs in the Infections and Infestations SOC that are SAEs,
- Opportunistic infections (OIs), as described below.

The MedDRA terms used to identify infections typically considered to be potential OIs are based on Winthrop et al. (2015) and are listed in [Appendix 7](#). The list contains relevant groupings of PTs, that is, narrow search terms and broad search terms, which together can assist in identifying subjects of interest. The list of terms is currently based on MedDRA version 19.1, but the list will be updated with each new version of MedDRA, including versions released after finalization of the statistical analysis plans but before database lock. For each of all infections and serious infections, the number and percentage of subjects overall and for each specific PT will be summarized by treatment, with specific event terms ordered by decreasing frequency in the total LY treatment group.

The number and percentage of subjects with TEAEs that are considered as OIs will be summarized by using PT nested within categories. For these TEAEs, the summary table will pool the narrow and broad terms together. Events will be ordered by decreasing frequency in the total LY treatment group.

These summaries will be presented for Safety Population Period 1, Safety Population Period 2, Safety Population All SC LY, and Safety Population All LY.

Visual techniques will be used to examine subjects experiencing treatment-emergent infectious AEs in the context of subject demographics, treatment group, treatment start and stop dates, infectious event, event start and stop dates, event severity and possible relationship to the study drug, total leukocytes, total lymphocytes, absolute neutrophils, event seriousness, event outcome, whether the subject was immunized for tuberculosis and/or herpes zoster, infecting agent, infection site, and whether anti-microbial treatment was recorded.

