Listeria monocytogenes (invasive disease only) (II)	Listeria encephalitis Listeria sepsis Meningitis listeria	Narrow
	Listeria test Listeria test positive Listeriosis	Broad
Tuberculosis (I)	Adrenal gland tuberculosis Bone tuberculosis Choroid tubercles Conjunctivitis tuberculous Cutaneous tuberculosis Disseminated Bacillus Calmette-Guerin infection Disseminated tuberculosis Ear tuberculosis Epididymitis tuberculous Extrapulmonary tuberculosis Female genital tract tuberculosis Immune reconstitution inflammatory syndrome associated tuberculosis Intestinal tuberculosis Joint tuberculosis Lupus vulgaris Lymph node tuberculosis Male genital tract tuberculosis Meningitis tuberculous Oesophageal tuberculosis Oral tuberculosis Pericarditis tuberculous Peritoneal tuberculosis Prostatitis tuberculous Pulmonary tuberculoma Pulmonary tuberculosis Renal tuberculosis Salpingitis tuberculous Silicotuberculosis Spleen tuberculosis Thyroid tuberculosis Tuberculoma of central nervous system	Narrow

Opportunistic Infection	Preferred Term (MedDRA Version 19.1)	Lilly-Defined Classification
	Tuberculosis Tuberculosis bladder Tuberculosis gastrointestinal Tuberculosis liver Tuberculosis of central nervous system Tuberculosis of eye Tuberculosis of genitourinary system Tuberculosis of intrathoracic lymph nodes Tuberculosis of peripheral lymph nodes Tuberculosis ureter Tuberculous abscess central nervous system Tuberculous endometritis Tuberculous laryngitis Tuberculous pleurisy Tuberculous tenosynovitis	
	Interferon gamma release assay Interferon gamma release assay positive Mycobacterium tuberculosis complex test Mycobacterium tuberculosis complex test positive Tuberculid Tuberculin test Tuberculin test false negative Tuberculin test positive	Broad
Nocardiosis (II)	Nocardia sepsis Nocardiosis	Narrow
	Nocardia test positive	Broad

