Nontuberculous mycobacterium disease (II)	Atypical mycobacterial infection Atypical mycobacterial lower respiratory tract infection Atypical mycobacterial lymphadenitis Atypical mycobacterium pericarditis Atypical mycobacterial pneumonia Borderline leprosy Bovine tuberculosis Indeterminate leprosy Leprosy Lepromatous leprosy Mycobacterial infection Mycobacterial peritonitis Mycobacterium abscessus infection Mycobacterium avium complex immune restoration disease Mycobacterium avium complex infection Mycobacterium chelonae infection Mycobacterium fortuitum infection Mycobacterium kansasii infection Mycobacterium marinum infection Mycobacterium ulcerans infection Superinfection mycobacterial	Narrow

Opportunistic Infection	Preferred Term (MedDRA Version 19.1)	Lilly-Defined Classification
	Tuberculoid leprosy Type 1 lepra reaction Type 2 lepra reaction	
	Atypical mycobacterium test positive Mycobacterial disease carrier Mycobacterium leprae test positive Mycobacterium test Mycobacterium test positive	Broad
Salmonellosis (invasive disease only) (II)	Aortitis salmonella Arthritis salmonella Meningitis salmonella Osteomyelitis salmonella Paratyphoid fever Pneumonia salmonella Salmonella bacteraemia Salmonella sepsis Typhoid fever	Narrow
	Salmonella test positive Salmonellosis	Broad
HBV reactivation (IV)	None	Narrow
	Asymptomatic viral hepatitis Chronic hepatitis B HBV-DNA polymerase increased Hepatitis B Hepatitis B antigen Hepatitis B antigen positive Hepatitis B core antigen Hepatitis B core antigen positive Hepatitis B DNA assay Hepatitis B DNA assay positive Hepatitis B DNA increased Hepatitis B e antigen Hepatitis B e antigen positive Hepatitis B surface antigen Hepatitis B surface antigen positive Hepatitis B virus test Hepatitis B virus test positive Hepatitis infectious Hepatitis post transfusion Hepatitis viral Withdrawal hepatitis	Broad
Herpes simplex (invasive disease only) (IV)	Colitis herpes Eczema herpeticum Gastritis herpes Herpes oesophagitis Herpes sepsis Herpes simplex colitis	Narrow

Opportunistic Infection	Preferred Term (MedDRA Version 19.1)	Lilly-Defined Classification

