	Herpes simplex encephalitis Herpes simplex gastritis Herpes simplex hepatitis Herpes simplex meningitis Herpes simplex meningoencephalitis Herpes simplex meningomyelitis Herpes simplex necrotising retinopathy Herpes simplex oesophagitis Herpes simplex pneumonia Herpes simplex sepsis Herpes simplex visceral Meningitis herpes Meningoencephalitis herpetic Meningomyelitis herpes Pneumonia herpes viral	
	Genital herpes Genital herpes simplex Herpes dermatitis Herpes ophthalmic Herpes pharyngitis Herpes simplex Herpes simplex DNA test positive Herpes simplex otitis externa Herpes simplex pharyngitis Herpes virus infection Nasal herpes Ophthalmic herpes simplex Oral herpes Proctitis herpes	Broad
Herpes zoster (any form) (II)	Disseminated varicella zoster vaccine virus infection Encephalitis post varicella Genital herpes zoster Herpes zoster Herpes zoster cutaneous disseminated Herpes zoster disseminated Herpes zoster infection neurological Herpes zoster meningitis Herpes zoster meningoencephalitis Herpes zoster meningomyelitis Herpes zoster necrotising retinopathy Herpes zoster oticus Herpes zoster pharyngitis Necrotising herpetic retinopathy Ophthalmic herpes zoster Varicella Varicella keratitis Varicella post vaccine	Narrow

Opportunistic Infection	Preferred Term (MedDRA Version 19.1)	Lilly-Defined Classification
	Varicella zoster gastritis Varicella zoster oesophagitis Varicella zoster pneumonia Varicella zoster virus infection	
	Varicella virus test Varicella virus test positive	Broad
Strongyloides (hyperinfection syndrome and disseminated forms only) (IV)	None	Narrow
	Strongyloidiasis	Broad
Paracoccidioides infections (V)	Paracoccidioides infection	Narrow
	None	Broad
Penicillium marneffeii (V)	Penicillium infection	Narrow
	None	Broad
Sporothrix schenckii (V)	Cutaneous sporotrichosis Sporotrichosis	Narrow
	None	Broad
Cryptosporidium species (chronic disease only) (IV)	Biliary tract infection cryptosporidial	Narrow
	Cryptosporidiosis infection Gastroenteritis cryptosporidial	Broad
Microsporidiosis (IV)	Microsporidia infection	Narrow
	None	Broad
Leishmaniasis (Visceral only) (IV)	Visceral leishmaniasis	Narrow
	Leishmaniasis	Broad
Trypanosoma cruzi infection (Chagas' Disease) (disseminated disease only) (V)	None	Narrow
	American trypanosomiasis Trypanosomiasis Meningitis trypanosomal	Broad
Campylobacteriosis (invasive disease only) (V)	Campylobacter sepsis	Narrow

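### The opportunistic-infection table pools narrow and broad search terms, so it gives a rate of potential OIs and does not show how many subjects had a narrow term

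*SAP*

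**What the plan says.** SAP 6.14.8.2 makes OIs one of three groups of treatment-emergent infection to be summarised. It introduces the term list cautiously: "The MedDRA terms used to identify infections typically considered to be potential OIs" are set out in Appendix 7, grouped as "narrow search terms and broad search terms, which together can assist in identifying subjects of interest". The table itself is described in firmer words: "The number and percentage of subjects with TEAEs that are considered as OIs will be summarized by using PT nested within categories". Then comes the pooling rule: "For these TEAEs, the summary table will pool the narrow and broad terms together".

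The table is planned for all four safety populations: Period 1, Period 2, All SC LY and All LY. Section 6.14.8.2 plans no count restricted to narrow terms. It describes no medical review that decides whether a subject with a broad term belongs in the category.

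Appendix 7 classifies every preferred term (PT) as Narrow or Broad within a named infection. Several headings restrict the infection. The herpes simplex heading, for example, reads "Herpes simplex (invasive disease only) (IV", and among its Broad terms are "Nasal herpes Ophthalmic herpes simplex Oral herpes Proctitis herpes".

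**The concern.** The wording moves from a search list for potential OIs to a count of subjects with events considered OIs, and nothing in between turns one into the other. A subject whose only event is oral herpes is counted, and is counted in a category whose heading is limited to invasive disease. The category figure can then contradict its own label.

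Period 1 is the only placebo-controlled safety comparison. If broad-only events occur there, they could make the pooled rates differ between groups when the narrow-term events do not, or blur a difference when the narrow-term events do differ. SAP 6.14 plans Fisher's exact tests and odds ratios for select categorical safety outcomes in Period 1. It does not say whether the OI count is among them, so the point concerns what the table can show and not a named test.

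**Working it through.** The SAP states no OI figure, so there is none to reproduce. The check sets the text of 6.14.8.2 against Appendix 7 and adds an illustration on assumed rates.

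**1. Headings against their Broad terms.** Six Appendix 7 headings are limited to invasive disease. Each has Broad terms that do not require it:

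| Heading limited to invasive disease | Example Broad term |
|---|---|
| Herpes simplex | Oral, Nasal and Genital herpes |
| Campylobacteriosis | Campylobacter gastroenteritis |
| Salmonellosis | Salmonellosis |
| Shigellosis | Shigella infection |
| Aspergillosis | Aspergillus infection |
| Listeria | Listeriosis |

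The first two rows name non-invasive events. The other four are unspecified terms that may or may not describe invasive disease. The herpes simplex category has 21 narrow and 14 broad PTs.

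**2. Can the narrow-term subject count be read from the PT rows?** Each row counts subjects with that PT, and a subject with two PTs appears in two rows. If two narrow rows show *a* and *b* subjects, the number with at least one of them lies between max(*a*, *b*) and *a* + *b*. With *a* = *b* = 1, that is 1 or 2 subjects. The count is fixed only when there is at most one non-zero narrow row. The same holds across categories for the overall count.

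**3. How far could the pooled rate sit from the narrow rate?** The planned size is 180 at 2:1:1:2 (Protocol 10.1), so combined LY in Period 1 is 180 × (2 + 1 + 1)/6 = 120 and placebo is 180 × 2/6 = 60. The documents give no OI rates. The rates below are assumptions, with narrow and broad-only events taken to occur in different subjects.

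Pooled rate = narrow rate + broad-only rate. Share with a narrow term = narrow rate / pooled rate.

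| Narrow | Broad-only | Pooled | Expected LY subjects counted (120 × pooled) | Share with a narrow term |
|---|---|---|---|---|
| 0.5% | 0% | 0.5% | 0.6 | 100% |
| 0.5% | 1% | 1.5% | 1.8 | 33% |
| 0.5% | 5% | 5.5% | 6.6 | 9% |
| 1% | 0% | 1% | 1.2 | 100% |
| 1% | 1% | 2% | 2.4 | 50% |
| 1% | 5% | 6% | 7.2 | 17% |
| 2% | 0% | 2% | 2.4 | 100% |
| 2% | 1% | 3% | 3.6 | 67% |
| 2% | 5% | 7% | 8.4 | 29% |

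The share depends entirely on the assumed rates. With no broad-only events, the pooled and narrow rates are equal and nothing is lost.

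**4. Comparison with the next section.** For hypersensitivity, SAP 6.14.8.3 reports a combined count on narrow and algorithmic terms (with the infusion-related reaction PT), then a narrow search and a broad search for each query separately. The SAP gives no reason for treating OIs differently.

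**The case against.** The case for leaving the plan alone has real weight.

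- **The terms are labelled as a search.** The SAP itself speaks of potential OIs, and a screen that favours sensitivity is a legitimate choice for safety. The table shows each PT within its category, so with Appendix 7 in hand a reader can tell oral herpes from herpes encephalitis. This stands. A reader might infer that the table is worthless as OI reporting, and the documents do not support that. What it lacks is the de-duplicated narrow-term count.
- **Subject-level review exists.** The same section plans visual examination of infectious events by site, agent, seriousness, outcome and anti-microbial treatment. That helps interpretation, but it does not decide who is counted.
- **Narrow does not mean confirmed.** Appendix 7 never defines it so. Oral candidiasis is Narrow, although its heading asks for oral disease not limited to the tongue. This stands, and it rules out treating narrow-term subjects as the true cases.
- **Bare test names are a weak example.** Appendix 7 lists "Tuberculid Tuberculin test Tuberculin test false negative Tuberculin test positive" as Broad, and a reader might infer that a routine skin test would be counted as an OI under an invasive-only heading. The tuberculosis heading carries no such restriction. A term counts only if it is reported as a treatment-emergent event. Protocol 9.5.3 has laboratory findings reported as adverse events when they are clinically significant and lead to a diagnosis. TB testing is scheduled only at screening. The section also states: "Infections will be defined using the PTs from the MedDRA Infections and Infestations SOC". How test-name terms fit that definition is not explained, but this is a minor issue.
- **Narrow-only counting would do harm.** HBV reactivation, HCV progression, Strongyloides, Trypanosoma cruzi, vibriosis and the non-specific fungal group have no narrow terms and would always show zero. Fungal sepsis and Listeriosis, both Broad, would leave the headline figure. This stands, and it shapes the fix.

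**Conclusion.** The concern holds in a limited form. As written, the OI table yields a rate of potential OIs found by term search. Its category counts can include events that fall outside their own headings, and the number of subjects with at least one narrow term is not shown and cannot in general be recovered from the rows.

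A reader might go further and conclude that most counted subjects would have no narrow-term OI, or that common infections will drive the rate. The documents do not support either claim: they give no frequencies, and any such share follows only from the rates one assumes. The distortion could be large, small or zero.

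The conclusion rests on the text of 6.14.8.2 and Appendix 7 and on the absence of any other planned narrow-term OI count. It is a cheap improvement to safety reporting. The primary analysis is unaffected.

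**What to change.** Replace the pooling sentence in SAP 6.14.8.2 so that the table gives, overall and for each Appendix 7 category:

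- (a) the number and percentage of subjects with any narrow term;
- (b) the number and percentage of subjects with any narrow or broad term, labelled as potential OIs.

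Keep the PT rows beneath. Do not present (a) as the sole OI count. For the six categories with no narrow terms, mark (a) as not applicable so that a structural zero is not read as an absence of events.

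The classification already exists in Appendix 7, so no new data are needed. The cost is the SAP wording and a few extra rows in an existing table, many of them with small counts.
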